10.5 Efficacy Assessments

10.5.1 Hospitalization and clinical events, clinical status, and environmental risk factors

All hospitalization events, procedures of special interest, and environmental risk factors will be listed.

The following data will be summarized by treatment using descriptive statistics:

• Duration of hospitalization (in days);

- Score on the NIAID ordinal scale at pre-specified time points;
- Score on the WHO ordinal scale at pre-specified time points;
- NEWS2 score at pre-specified time points.

The following data will be summarized by treatment using frequency tables:

- Proportion (percentage) of participants admitted to ICU;
- Proportion (percentage) of participants requiring mechanical ventilation;
- Proportion (percentage) of participants with at least a 2 point improvement on the NIAID scale or live discharge from hospital from baseline at any time during the study;
- Proportion (percentage) of participants with at least a 2-point improvement on the WHO ordinal scale or live discharge from hospital from baseline at any time during the study;
- Proportion (percentage) of participants with any worsening on the NIAID ordinal scale from baseline to Day 15;
- Proportion (percentage) of participants with at least a 2-point worsening on the NIAID ordinal scale from baseline at any time during the study;
- Consciousness level score assessed by NEWS2;
- Severity of pre specified clinical events (fever, cough, and shortness of breath).

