9.4.1. General Considerations

Method	Analysis
Descriptive Statistics	number of participants, mean, standard deviation,
	median, minimum, and maximum for continuous
	measures, and frequency counts and percentages for
	categorical measures
Kaplan-Meier curves and summary statistics	Time-to-event analysis
Logistic regression analysis	Treatment comparisons of binary variables with
	treatment in the model.
Nonparametric	Treatment comparison of ordinal variables.
(for example, Mann-Whitney or van Elteren tests)	
Analysis of variance or analysis of covariance	Treatment comparisons of continuous variables
	following appropriate transformations, if necessary

This table describes the general statistical methods that may be used in this study.

Adjustments for other factors, if any, will be described in the SAP.

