9.4.4. Exploratory Endpoints

Exploratory endpoints will be summarized using descriptive methodology and treatment comparisons conducted using methods previously described.

Endpoints will include:

- Duration (days) of hospitalization
- Proportion (percentage) of participants admitted to ICU
- Proportion (percentage) of participants requiring mechanical ventilation
- Score on the NIAID ordinal scale at pre-specified time points
- Score on the WHO ordinal scale at pre-specified time points
- Proportion (percentage) of participants with at least a 2-point improvement on the WHO ordinal scale or live discharge from hospital, at pre-specified time points
- Proportion (percentage) of participants with at least a 2-point improvement on the NIAID ordinal scale or live discharge from hospital at pre-specified time points
- NEWS2 score at pre-specified time points
- Proportion (percentage) of participants with any worsening on the NIAID ordinal scale from baseline to Day 15, and
- Comparison from baseline to Day 29 for the emergence of viral resistance to LY3819253.

Mortality and categorical changes on the ordinal scale will be analyzed as discrete variables.

Additional exploratory analyses of the data will be conducted as deemed appropriate. Study results may be pooled with the results of other studies for safety, pharmacodynamic, or

population PK analysis purposes to avoid issues with post-hoc analyses and incomplete disclosures of analyses.

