10. STATISTICAL METHODOLOGY

10.1 General

Data listings will be provided for all data that is databased. Summary statistics and statistical analysis will only be presented for data where detailed in this SAP. For continuous data, summary statistics will include the arithmetic mean, arithmetic standard deviation (SD), median, min, max and N; for log-normal data (e.g. the PK parameters: AUCs and maximum observed drug concentration $[C_{max}]$) the geometric mean and geometric coefficient of variation (CV%) will also be presented. For categorical and ordinal data, frequency count and percentages will be presented. Data listings will be provided for all participants up to the point of withdrawal, with any participants excluded from the relevant population highlighted. Summary statistics and statistical analyses will generally only be performed for participants included in the relevant analysis population. For the calculation of summary statistics and statistical analysis, unrounded data will be used.

Mean change from baseline is the mean of all individual participants' change from baseline values. Each individual change from baseline will be calculated by subtracting the individual participant's baseline value from the value at the timepoint. The individual participant's change from baseline values will be used to calculate the mean change from baseline using a SAS procedure such as Proc Univariate.

Data analysis will be performed using SAS[®] Version 9.4 or greater.

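### Duration of hospitalization is summarised as raw days with no rule for in-hospital deaths or stays still open at Day 60, so a death carries no penalty and early deaths can make an arm look better

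*SAP*

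**What the plan says.** The protocol (Section 3 and Section 9.4.4) and SAP 5.3 name the endpoint "Duration (days) of hospitalization" and class it as exploratory. SAP 10.5.1 places "Duration of hospitalization (in days" under this instruction: "The following data will be summarized by treatment using descriptive statistics". SAP 10.1 says what that means: "For continuous data, summary statistics will include the arithmetic mean, arithmetic standard deviation (SD), median, min, max and N".

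On treatment comparisons, protocol 9.4.4 says "Exploratory endpoints will be summarized using descriptive methodology and treatment comparisons conducted using methods previously described". The general methods in protocol 9.4.1 pair analysis of variance or covariance with "Treatment comparisons of continuous variables", and offer "Kaplan-Meier curves and summary statistics" for time-to-event data, all as methods that may be used. The SAP assigns a Kaplan-Meier plot only to viral clearance (10.4.2).

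On death, protocol 9.4.4 says "Mortality and categorical changes on the ordinal scale will be analyzed as discrete variables". SAP 10.5.1 contains no mortality summary. SAP 14.2, on missing data, concerns only what is displayed in listings.

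No section of either document defines the start or end of the stay for this endpoint, the value given to an in-hospital death, or the treatment of a stay that outlasts follow-up.

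**The concern.** A stay can end by discharge or by death, and the two mean opposite things. Raw days do not separate them. Someone who dies on day 5 contributes a 5-day stay, or nothing at all if the programmer needs a discharge date and finds none. Either way the worst outcome is not counted against the arm.

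Death is foreseeable here: protocol 2.2 says the disease can be fatal, and inclusion criterion 2 admits severe illness. The distinction was also made elsewhere in the same SAP section, where the 2-point-improvement endpoints require discharge alive. Duration of stay has no such qualifier.

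At stake is a by-arm table that could show shorter stays in an arm with more early deaths. Protocol 9.4.4 would also allow that table to be turned into a treatment comparison.

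**Working it through.** The documents give no figure for duration of stay, mortality or time to death, so there is no stated figure to reproduce. The inputs below are assumptions chosen to show direction and rough size.

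**Inputs (assumed)**
- Survivor stay S: gamma, shape 2, mean 12 days, counted from Day 1.
- Mortality q: 5% in one arm, 25% in the other; all deaths in hospital.
- Time to death: exponential with mean D of 6, 12 or 20 days.
- Day 60 and Day 29 are visits in the protocol's Schedule of Activities. Cutting stays at Day 60 is my assumption, not a rule in the plan.

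**Raw mean, death counted as the end of the stay**

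Mean = (1 − q) × 12 + q × D.

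| D (days) | q = 5% | q = 25% | Change |
|---|---|---|---|
| 6 | 0.95 × 12 + 0.05 × 6 = 11.7 | 0.75 × 12 + 0.25 × 6 = 10.5 | −1.2 |
| 12 | 0.95 × 12 + 0.05 × 12 = 12.0 | 0.75 × 12 + 0.25 × 12 = 12.0 | 0 |
| 20 | 0.95 × 12 + 0.05 × 20 = 12.4 | 0.75 × 12 + 0.25 × 20 = 14.0 | +1.6 |

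A cut at Day 60 matters only in the last row. The mean time to death becomes 20 × (1 − e^−3) = 19.0, and the row becomes 12.35 and 13.75, a change of +1.4. The raw summary therefore misleads when deaths come earlier than the typical survivor stay, says nothing when they coincide, and moves the right way when deaths come later.

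**Raw mean, deaths left out**

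The mean is 12 in both arms at any q under these inputs. Mortality disappears from the summary.

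**Days alive and out of hospital to Day 29, with 0 for deaths**

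For survivors the mean of max(29 − S, 0) is 29 − 12 + 0.33 = 17.33, where 0.33 = 6 × e^(−29/6) × (2 + 29/6) is the mean stay beyond 29 days. A participant who dies in hospital has 0 whatever the day, so D drops out.
- q = 5%: 0.95 × 17.33 = 16.5
- q = 25%: 0.75 × 17.33 = 13.0

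This falls by 3.5 days, the right direction, at all three values of D.

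**One arm of six (assumed stays)**

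Six is the planned active arm in each of Cohorts 1-3. Take survivors' stays of 6, 8, 10, 12, 14 and 30 days, then let the 30-day participant die on day 5 instead.

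| Handling | Mean | Median |
|---|---|---|
| All alive | 80/6 = 13.3 | 11 |
| Death counted as 5 days | 55/6 = 9.2 | 9 |
| Death left out | 50/5 = 10.0 | 10 |
| Death set to Day 60 | 110/6 = 18.3 | 11 |

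Both default calculations make the arm look better after the death.

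**The case against.** The strongest reply is that the plan is silent rather than wrong. A reader might infer that the SAP instructs deaths to be counted as short stays, that it cuts stays at Day 60, or that raw duration always favours the arm with more deaths. The documents support none of these. SAP 10.5.1 does not say that death ends the stay. Protocol 4.1 limits weekly in-hospital assessments to Day 60 but sets no truncation rule for this endpoint. The direction depends on timing, as shown above. SAP Section 3 also refers to table shells that are not in the documents, and a derivation note could sit there. This stands, and the point is confined accordingly.

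Second, very early deaths may be uncommon. Exclusion criteria 10, 13, 16 and 21 remove participants with required or impending invasive ventilation, recent pressor use, a comorbidity considered life-threatening within 29 days, or room-air SpO2 below 88%. This is a fair reason not to rely on the 6-day scenario alone, but the documents give no death timing that would settle it.

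Third, the effect is small against noise. The assumed survivor stay has SD 12/√2 = 8.5 days, so the standard error of a difference is 8.5 × √(2/6) = 4.9 days at 6 versus 6, and 8.5 × √(2/50) = 1.7 days at 50 versus 50. The 1.2-day shift is below both. The endpoint is exploratory, and no power statement or SAP test uses it. This stands as a limit on importance.

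Fourth, deaths are to be seen elsewhere: the protocol analyses mortality as a discrete variable, SAP Section 12 declares no departures from the protocol, and SAP 10.5.1 reports ordinal-scale worsening. These reduce the chance of misreading but do not repair the duration summary, and SAP 10.5.1 itself lists no mortality table to set beside it.

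**Conclusion.** The point holds as a gap in the definition with a foreseeable consequence. As planned, duration of stay is raw days, and neither document has a rule for in-hospital deaths or for stays open at Day 60. The natural calculations give a death no penalty. If deaths come earlier than the typical survivor stay, an arm with more of them can look better; if they come later, the raw mean moves the other way.

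The size rests on assumed inputs. With a 20-point mortality difference and a mean survivor stay of 12 days, the raw mean shifts by −1.2, 0 or +1.4 days for mean times to death of 6, 12 and 20 days (stays cut at Day 60), whereas days alive and out of hospital falls by 3.5 days each time.

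The impact is modest in Cohorts 1-3, with six participants per active arm and no SAP inferential test. It is larger if optional Cohort 4 runs with up to 100 participants, since protocol 4.2 gives that cohort a clinical-worsening purpose. The change should be made, but nothing about the primary safety objective depends on it.

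**What to change.** In SAP 10.5.1, replace the raw-days summary with one of these:

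- days alive and out of hospital from Day 1 to Day 29, set to 0 for anyone who dies by Day 29; or
- time to live discharge, with deaths kept as never discharged and participants still in hospital censored at Day 60.

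With either choice, state whether days in an extended care facility count as out of hospital and show the number of deaths per arm beside the summary. Keep raw duration in survivors as a supplement only, and state there whether the stay starts at admission or Day 1.

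The cost is SAP wording and a short derivation. Protocol 8.2.5 already records dates of admission, discharge and transfer to extended care. It does not list the date of death among hospitalization events, so the team should confirm that the case report form captures it. The downside is that the composite is slightly less direct to read than days in hospital.

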12. CHANGES FROM THE PROTOCOL SPECIFIED STATISTICAL ANALYSES

There were no changes from the protocol specified statistical analyses.

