14.2 Missing Data

Missing data will not be displayed in listings.

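### The mechanical-ventilation and ICU proportions have no rule for death, so unbalanced deaths without the event could make the worse arm look better (inexpensive improvement, exploratory endpoints)

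*SAP*

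**What the plan says.** SAP section 10.5.1 introduces a list with "The following data will be summarized by treatment using frequency tables". Two of its items are ICU admission and the "Proportion (percentage) of participants requiring mechanical ventilation". Neither item has a time window, a named analysis population or a rule for death.

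Protocol section 9.4.4 lists the same two endpoints in equally bare form. It adds "Exploratory endpoints will be summarized using descriptive methodology and treatment comparisons conducted using methods previously described", and the methods table in protocol section 9.4.1 offers logistic regression for binary variables. It also states "Mortality and categorical changes on the ordinal scale will be analyzed as discrete variables".

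The SAP text available for review contains no mortality summary, yet SAP section 12 says "There were no changes from the protocol specified statistical analyses". The missing-data text in SAP section 14.2 is one line about listings: "Missing data will not be displayed in listings".

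Elsewhere in the same SAP list death is dealt with, at least in part. The improvement endpoint counts "at least a 2 point improvement on the NIAID scale or live discharge from hospital from baseline at any time during the study", so a participant whose hospital stay ends in death does not qualify through discharge.

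**The concern.** Death before intubation, or before ICU transfer, prevents the event from being observed. In a simple proportion such a participant falls into the favourable category. An arm with more deaths of this kind would then show a lower ventilation or ICU proportion because its participants did worse.

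The protocol plans treatment comparisons of exploratory endpoints, so the two arms' figures will be set against each other.

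The adverse event tables are not a dependable backstop. Protocol section 10.3.1 exempts COVID-19 respiratory failure needing invasive ventilation from AE reporting unless the investigator judges it related to the intervention. It also exempts disease progression that is no more severe than expected. Section 10.3.2 says an event that is not an AE cannot be an SAE.

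**Working it through.** **Is there a figure to reproduce?** No. The documents give no rate, sample size or power for either proportion. The only powered clinical outcome is worsening on the NIAID scale (22% to 9%), which is a different endpoint. What follows is therefore arithmetic on the definition, with assumed counts.

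**Inputs from the documents**
- Baseline: exclusion criterion 10 removes anyone who needs, or is about to need, invasive ventilation. Participants therefore start without the ventilation event.
- Denominator: not named. The Safety population (SAP section 9) is all randomized and dosed participants, so those who die stay in it. I assume it applies.
- Arm size: Cohort 4 has up to 100 participants at about 1:1, so up to 50 per arm. Cohorts 1 to 3 have 6 on LY3819253 at each dose.

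**Formulas.** Let v be the proportion ventilated and u the proportion who die unventilated.
- Planned row: v.
- Ventilation or death: v + u.
- The apparent advantage disappears when the excess of u on LY3819253 equals its reduction in v, and reverses when the excess is larger.
- One unventilated death is worth 1/50 = 2 points at 50 per arm, and 1/6 = 16.7 points at 6 per arm.

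**Assumed counts, 50 per arm**

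| Scenario | Placebo: ventilated + unventilated deaths | LY3819253: ventilated + unventilated deaths | Planned row, placebo v LY3819253 | Ventilation or death, placebo v LY3819253 |
|---|---|---|---|---|
| Deaths balanced | 8 + 1 | 6 + 1 | 16% v 12% | 9/50 = 18% v 7/50 = 14% |
| Benefit vanishes | 5 + 2 | 3 + 4 | 10% v 6% | 7/50 = 14% v 7/50 = 14% |
| Reversal | 8 + 1 | 6 + 5 | 16% v 12% | 9/50 = 18% v 11/50 = 22% |

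In the first row both measures differ by 4 points, so nothing is distorted. In the second, an apparent relative reduction of 1 − 6/10 = 40% corresponds to no difference once death is counted. In the third, a 4-point advantage becomes a 4-point disadvantage.

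**Would dropping those deaths from the denominator help?** Not in the reversal scenario: 8/49 = 16.3% v 6/45 = 13.3% still favours LY3819253.

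**Would a separate mortality table be enough?** Not by itself. Suppose 6 of 50 are ventilated and 5 of 50 die. The number who died unventilated could then be anything from 0 to 5, so ventilation or death could be anything from 6/50 = 12% to 11/50 = 22%. The two separate totals do not fix the overlap.

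The same reasoning applies to ICU admission, with death before admission in place of death before ventilation.

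**The case against.** The strongest case against has four parts.

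1. **The counting is inferred from silence.** A reader might conclude that the plan decides to treat unventilated deaths as good outcomes. No sentence says so. The word requiring is undefined, and Appendix 8 of the protocol recognises respiratory failure where the need exists but the therapy cannot be given because of resource limits. A participant who needed ventilation but did not receive it might be counted. This stands: the defect is a missing rule, not a stated wrong one.

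2. **Little hangs on the endpoint.** It is exploratory, protocol section 9.1 treats all testing as exploratory without multiplicity adjustment, and the SAP only tabulates this item. No dose decision or power statement in the documents uses it. A reader might infer that ventilation is the outcome the drug is chiefly meant to reduce. The documents do not support that: they speak of reducing viral replication and mitigating disease severity, and Cohort 4 is sized on NIAID worsening. This stands and limits the weight of the point.

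3. **Death may be visible elsewhere.** The protocol promises a mortality analysis, the SAP tabulates NIAID and WHO scores, and the table shells mentioned in SAP section 3 are not available here. This stands in part. The scale categories are not reproduced, so it cannot be confirmed that they score death, and a mortality total alone does not identify unventilated deaths.

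4. **The rates are assumed.** This stands. With balanced deaths there is no distortion, and the vanishing and reversal scenarios need more unventilated deaths on LY3819253 alongside less ventilation. Nothing in the documents says that this is likely.

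**Conclusion.** The point holds as an inexpensive improvement to exploratory endpoints. The ventilation and ICU proportions have no rule for death, and no text available for review supplies one. On the plain definition with a Safety-type denominator, a death without the event is a non-event.

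Whether this biases the comparison depends on whether such deaths are unbalanced between arms, and the documents give no rates from which to judge. Under the assumed counts the effect ranges from none to a reversal of a 4-point difference. The documents do not support the stronger readings, that the proportion will be misleading or that the trial's main conclusions are at risk. The conclusion rests on three assumptions: that the Safety population is used, that requiring means receiving, and that the table shells add no rule.

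**What to change.** In SAP section 10.5.1:

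- Define the ventilation event (received, or needed), use the Safety population, and state one window for all rows. Day 29 and Day 60 are both possible; the documents give none, so the choice is the sponsor's. The Schedule of Activities marks clinical status at Day 60 but does not mark hospitalization events there, which makes Day 29 simpler for ICU admission.
- Tabulate mechanical ventilation or death by treatment, counting each participant once, with ventilation and death without ventilation as component rows.
- Do the same for ICU admission.
- Add the mortality summary promised in protocol section 9.4.4, or record its omission in SAP section 12. Align the endpoint wording in protocol section 9.4.4 at the next amendment.

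The cost is a few table rows and some SAP wording. Ventilation and ICU admission are already recorded (protocol sections 8.2.5 and 8.2.6). Death is not named among those items, so the team should confirm that the CRF captures its date for every participant, including deaths not reported as AEs; the promised mortality analysis needs this anyway. The downside is that a composite mixes events of different gravity and must be read with its components.

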More detailed information about the known and expected benefits and risks and reasonably expected adverse events of LY3819253 may be found in the IB.

3. Objectives and Endpoints

Objectives	Endpoints
Primary	
Characterize the safety and tolerability of LY3819253 after intravenous infusion	• Safety assessments such as AEs and SAEs
Secondary	
Characterize the pharmacokinetics of LY3819253 after intravenous infusion	• LY3819253 mean concentration on Day 29
Characterize the pharmacodynamics of LY3819253 after intravenous infusion	 Change from baseline in SARS-CoV-2 viral load (Days 7, 11, 15 and 22) SARS-CoV-2 viral load AUC Time to SARS-CoV-2 clearance
Tertiary/Exploratory	
Characterize the participant's clinical status	 Duration (days) of hospitalization Proportion (percentage) of participants admitted to ICU Proportion (percentage) of participants requiring mechanical ventilation Score using the NIAID and WHO ordinal scales at pre-specified time points Proportion (percentage) of participants with at least a 2-point improvement on the NIAID and WHO ordinal scale or live discharge from hospital at pre-specified time points NEWS2 score at pre-specified time points Proportion (percentage) of participants with any worsening on the NIAID ordinal scale from baseline to Day 15
Characterize the pharmacodynamics of LY3819253 after intravenous infusion	Proportion of participants that achieve SARS- CoV-2 clearance (Days 7, 11, 15, 22)
Characterize emergence of viral resistance to LY3819253	Comparison from baseline to Day 29

Abbreviations: AE = adverse event; ICU = intensive care unit; NIAID = National Institute of Allergy and Infectious Diseases; NEWS2 = National Early Warning Score; SAE = serious adverse event; SARS-CoV-2 = severe acute respiratory syndrome coronavirus 2; WHO = World Health Organization.

4. Study Design

4.1. **Overall Design**

Study PYAA is a Phase 1, double-blind, sponsor unblinded, randomized, placebo-controlled, single-ascending dose study.

Screening

Interested hospitalized participants will sign the appropriate informed consent document(s) prior to completion of any procedures. Screening may be performed up to 48 hours prior to dosing. Screening and Day 1 may occur on the same day.

Double-blind Treatment and Assessment Period

This is the general sequence of events during the treatment and assessment period:

- Participants are randomized to LY3819253 or placebo
- Site completes baseline procedures and sample collection

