5.3 Exploratory Endpoints

- Duration (days) of hospitalization.
- Proportion (percentage) of participants admitted to intensive care unit (ICU).
- Proportion (percentage) of participants requiring mechanical ventilation.
- Score using the National Institute of Allergy and Infectious Diseases (NIAID) and World Health Organization (WHO) ordinal scale or live discharge from hospital at pre-specified time points.
- National Early Warning Score (NEWS2) score at pre-specified time points.
- Proportion (percentage) of participants with at least a 2-point improvement on the NIAID and WHO ordinal scale or live discharge from hospital at pre-specified time points.
- NEWS2 score at pre-specified time points.
- Proportion (percentage) of participants with any worsening on the NIAID ordinal scale from baseline to Day 15.
- Proportion of participants that achieve SARS-CoV-2 clearance (Days 7, 11, 15, 22).
- Emergence of viral resistance to LY3819253 from baseline to Day 29.

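### SAP 10.5.1 counts 2-point improvement or live discharge over the whole study, but the protocol and SAP 5.3 set it at fixed time points, and SAP 12 declares no change

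*SAP*

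**What the plan says.** Four places set the timing of this endpoint, and a fifth bears on whether a change was declared.

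- **Protocol Section 3** (exploratory objectives): "2-point improvement on the NIAID and WHO ordinal scale or live discharge from hospital at pre-specified time points".
- **Protocol 9.4.4**, NIAID bullet: "2-point improvement on the NIAID ordinal scale or live discharge from hospital at pre-specified time points". The WHO bullet has the same timing: "ordinal scale or live discharge from hospital, at pre-specified time points".
- **SAP 5.3**: "at least a 2-point improvement on the NIAID and WHO ordinal scale or live discharge from hospital at pre-specified time points".
- **SAP 10.5.1**, NIAID row: "2 point improvement on the NIAID scale or live discharge from hospital from baseline at any time during the study". The WHO row counts a gain of at least 2 points on the WHO "ordinal scale or live discharge from hospital from baseline at any time during the study".
- **SAP 12**: "There were no changes from the protocol specified statistical analyses".

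SAP Section 3 says that the SAP supersedes the protocol's statistical considerations and that substantial differences will be identified. Protocol 4.1 places the last follow-up assessment at Day 60. Neither document lists the pre-specified time points for this endpoint, and neither gives an expected improvement or discharge rate.

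**The concern.** Status at a named visit and ever having improved are different quantities. The first can go up or down from one visit to the next. The second can only rise with follow-up. As worded in SAP 10.5.1, a single transient 2-point gain or any live discharge up to Day 60 is a permanent success, even if relapse or death follows.

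Because the SAP takes precedence and declares no change, the any-time table would be the one produced, and a reader of the study report would take it for the protocol endpoint. Protocol 9.4.4 also foresees treatment comparisons on the exploratory endpoints, so the SAP wording decides what would be compared. A cumulative proportion over a long window tends to converge between arms when most participants eventually recover. A difference in the speed of recovery would then look smaller in this table than at an earlier fixed visit.

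**Working it through.** **1. Is the mismatch real?** The plan states no figure for this endpoint that could be reproduced, so the first check is textual.

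| Place | Scale | Timing |
|---|---|---|
| Protocol 3 | NIAID and WHO | fixed time points |
| Protocol 9.4.4 | NIAID; WHO | fixed time points |
| SAP 5.3 | NIAID and WHO | fixed time points |
| SAP 10.5.1 | NIAID; WHO | any time in the study |

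It does not look like loose shorthand. SAP 10.5.1 itself keeps fixed time points for the raw NIAID, WHO and NEWS2 scores, and keeps Day 15 for any NIAID worsening. Nor is it explained by the SAP having been written against Amendment (a): the change table of the current amendment lists no change to Protocol Section 3 or 9.4.4, and SAP 5.3 carries the fixed-time wording.

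**2. How much could it matter?** This part rests on assumptions. Let the time to first improvement or live discharge be exponential, with placebo median m days and hazard ratio 1.5 in favour of treatment. The proportion counted by day t is

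- placebo: 1 − 2^(−t/m)
- treated: 1 − 2^(−1.5t/m)

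For m = 10 at Day 15: placebo 1 − 2^(−1.5) = 64.6%, treated 1 − 2^(−2.25) = 79.0%. By Day 60: placebo 1 − 2^(−6) = 98.4%, treated 1 − 2^(−9) = 99.8%.

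| Placebo median (days) | Day 15, placebo vs treated | Difference (points) | Day 60, placebo vs treated | Difference (points) |
|---|---|---|---|---|
| 10 | 64.6% vs 79.0% | 14.3 | 98.4% vs 99.8% | 1.4 |
| 15 | 50.0% vs 64.6% | 14.6 | 93.8% vs 98.4% | 4.7 |
| 20 | 40.5% vs 54.1% | 13.6 | 87.5% vs 95.6% | 8.1 |

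Differences are taken before rounding. Both columns count first events cumulatively, so the table isolates the effect of the longer window. Relapse and death after improvement are not modelled.

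**3. How close to a ceiling?** Let p be the control proportion at Day 15 and d the share who never improve. Then the Day 60 proportion is (1 − d) × [1 − (1 − p)^4], because 60/15 = 4, and the Day 15 proportion is (1 − d) × p.

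- d = 0, p = 40/50/60/70/80%: 87/94/97/99/99.8% by Day 60.
- d = 10%, same p: 78/84/88/89/90% by Day 60.

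Across these cases, with rate ratios of 1.3 and 1.5, the treatment difference is 7 to 15 points at Day 15 and 0.1 to 8 points by Day 60.

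**4. Does power always fall?** No. Take 56 placebo and 68 LY3819253 participants (50 + 6 and 50 + 18, with a full Cohort 4), one-sided alpha 0.05, rate ratio 1.5 and d = 0. Power then goes from 54% at Day 15 to 28% by Day 60 when p = 60%, but from 44% to 50% when p = 40%. The difference in points still shrinks in the second case, from 13.5 to 8.3.

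**The case against.** The strongest reply is that little depends on this row. The endpoint is exploratory. Protocol 9.1 makes any testing exploratory and unadjusted for multiplicity, and SAP 10.5.1 plans only frequency tables for it. No sample size, dose decision or stopping rule uses it: the clinical power statement concerns NIAID worsening to Day 15, whose timing SAP 10.5.1 keeps. All of this stands and limits the weight of the point.

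A reader might go further and infer three things that the documents do not support.

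- **That nearly everyone will count as improved by Day 60.** No improvement or discharge rate is given. The assumptions above put the control proportion anywhere from about 78% to almost 100%. Excluding participants who need or are about to need invasive ventilation makes many discharges plausible, but it does not fix a rate.
- **That an effect on speed of recovery would be invisible.** With a 20-day median, 8.1 points remain by Day 60. SAP 10.5.1 also summarizes duration of hospitalization and the NIAID, WHO and NEWS2 scores at fixed times.
- **That late deterioration is hidden.** The same section tabulates a NIAID worsening of 2 points or more at any time, any worsening to Day 15, ICU admission and mechanical ventilation, and lists all hospitalization events. Protocol 9.4.4 adds mortality as a discrete variable. Relapse is masked within the improvement rows, not across the outputs.

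It is also fair to say that the separate table shells, which are not among the documents, may name the visits, and that discharge at a time point could be read as cumulative discharge by that day. Neither argument reconciles SAP 10.5.1 with SAP 5.3, or makes the statement in SAP 12 correct.

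**Conclusion.** The mismatch is certain for both scales. As written, SAP 10.5.1 would report a cumulative any-time endpoint in place of the fixed-time endpoint in Protocol Sections 3 and 9.4.4 and SAP 5.3, and SAP 12 is wrong to report no changes.

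The numerical consequence is a risk, not a finding. It depends on the assumed recovery rate, the exponential form and the hazard ratio of 1.5. The loss of contrast between Day 15 and Day 60 is 12.9 points for a 10-day median (14.3 − 1.4) but 5.5 points for a 20-day median (13.6 − 8.1). A ceiling is possible but not established. The point should be corrected because the reported endpoint would not be the stated one and the repair is cheap, but no main conclusion of the trial depends on it.

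**What to change.** In SAP 10.5.1, change the timing of both improvement rows to the fixed-time wording of SAP 5.3 and name the scheduled visits. Days 7, 15 and 29 are one example for the sponsor to confirm; they are not taken from the documents as the time points for this endpoint.

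State that a participant who has died by the visit counts as not improved, and state whether live discharge is scored as status on that day or cumulatively up to it. If the any-time version is wanted, keep it as a labelled supplement and declare it in SAP 12.

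The cost is SAP wording and a table shell. The Schedule of Activities already collects clinical status and hospitalization events at Days 7, 15 and 29, so no new data are needed.
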